#### 1. OBJECTIVES

# 1.1. Primary Objectives:

- **1.1.1.** To characterize the safety and tolerability of CB-103 in combination with Venetoclax in adolescent (12 to 18 years) and adult (19 to 60 years) patients with relapsed/refractory T-cell acute lymphoblastic leukemia (T-ALL) and T-cell lymphoblastic lymphoma (T-LBL).
- **1.1.2**. To assess the efficacy of CB-103 in combination with venetoclax by the overall response rate (ORR), defined as complete remission (CR) plus CR with incomplete blood count recovery (CRi) [1] plus partial remission (PR) [2], in adolescent and adult patients with relapsed/refractory T-ALL/T-LBL.

# 1.2. Secondary Objectives:

- **1.2.1.** To assess whether the ORR to CB-103 in combination with Venetoclax is dependent on pre-treatment expression of Notch and/or BCL2 pathway.
- **1.2.2.** To determine the preliminary assessment of CB-103 in combination with Venetoclax by other efficacy parameters such as minimal residual disease (MRD), duration of response (DoR), overall survival (OS), and event-free survival (EFS) in adolescent and adult patients with relapsed/refractory T-ALL/T-LBL.

# 1.3. Exploratory Objectives:

- **1.3.1.** To explore potential correlations of ORR to treatment and additional pharmacodynamic (PD) markers, i.e., other oncogenic pathway activations that may co-occur at the start of treatment.
- **1.3.2.** To evaluate how many patients are able to transition to Hematopoietic Stem Cell Transplant (HSCT):
  - **1.3.2.1.** Either in the patients achieving CR after the induction and reinduction cycles; **1.3.2.2.** Or in the patients with PR or stable disease (SD) after the induction and reinduction.

# 2. BACKGROUND AND RATIONALE

# 2.1. T-ALL Background

Approximately 15% and 25% of newly diagnosed cases of acute lymphoblastic leukemia (ALL) in children and adults, respectively, are T-cell ALL (T-ALL) and are historically linked with a poor prognosis [1,2]. T-ALL is characterized by an older age of onset than B-ALL, male sex preponderance, and inferior outcome in comparison to B-ALL [1]. Even with the most advanced treatment, the 5-year disease-free survival (EFS) of children is only around 75%, with about 30% of children with T-ALL still failing to respond, relapsing, or dying from the disease [3]. Traditional treatment regimens for adult acute lymphoblastic leukemia, including allogeneic hematopoietic cell transplantation, result in overall survival of approximately 40% [4].

# 2.2. Notch pathway and Notch inhibitors in T-ALL

In T-ALL, the most frequent actionable mutation is Notch1 [5]. Notch pathway signaling is commonly activated by Notch1 and FBXW7 gene mutations in T-cell ALL, and these are the most commonly mutated genes in pediatric T-cell ALL [Board P D T IN. Childhood acute lymphoblastic leukemia treatment (PDQ®)[M]//PDQ Cancer Information Summaries. National Cancer Institute (US), 2019].[15,148] Notch1-activating gene mutations occur in approximately 50% to 60% of T-cell ALL cases, and FBXW7-inactivating gene mutations occur in approximately 15% of cases, with the result that approximately 60% of cases have Notch pathway activation by mutations in at least one of these genes [6]. In T-ALL Notch1 and the strictly associated  $\gamma$ -secretase inhibitors were tested in late-stage

Protocol 2021-0547 4/25/2024

disease, with some responses of short duration and considerable gut toxicity [7]. The best study reported one CR and an overall 32% response rate in 25 patients with relapsed disease [8].

#### 2.3. CB-103

#### 2.3.1. Preclinical studies

CB-103 is a first-in-class small molecule pan-Notch inhibitor with a novel mechanism of action directly targeting the Notch transcriptional activation complex by inhibition of the NICD-CSL interaction [9]. In contrast to the aforementioned inhibitors, pan-Notch inhibitor CB-103 is binding to the Notch-specific transcription complex in the cell nucleus and unfolds its effects at the transcription level of Notch target genes at the most downstream and central location. Thereby CB-103 can inhibit transcriptional activation of Notch-related target genes, regardless of the mechanism of activation, at the most downstream location in the cell nucleus.

Pharmacodynamic (PD) and direct effect of CB-103 treatment on tumor proliferation and growth was studied ex vivo in 10 primary T-ALL patient blood samples and based on one of the Notch positive T-ALL patient samples in vivo in a patient derived (PDx) xenograft model of human T-ALL in NSG mice. CB-103 was shown to be effective both against primary human T-ALL samples ex vivo and in patients' derived T-ALL xenografts in mice.

In a pre-clinical study the potential additive or synergistic activity of CB-103 in combination chemotherapy agents was investigated in patient samples harbouring GOF mutations in NOTCH1 receptor. The effect of drug on cell proliferation/ cell death was determined by MTS and best dose/combination were confirmed by flow cytometry using Annexin V+ 7AAD staining or an alternative method.

Combination drugs tested were:

- a. Nelarabine
- b. Cytarabine
- c. Gemcitabine
- d. HDAC6 inhibitor (ACY1215)
- e. Dexamethasone
- f. Vincristine

The data revealed that in NOTCH mutated (GOF) T-ALL patient samples, CB-103 exhibit synergy with Cytarabine, Gemcitabine, Nelarabine, HDAC6 inhibitor and Vincristine (**Table 1**). This synergy between CB-103 and different chemotherapeutic agents enhances cell death in NOTCH + T-ALL leukemic blasts.

More interestingly, a synergy between CB-103 and Cytarabine, Gemcitabine, and Nelarabine was observed also in one of the two patients with Notch wild-type T-ALL.

Page | 5 04/25/2024

**Table 1:** Summary of drug combination effect on primary T-ALL samples:

T-ALL	NOTCH	Additional	Со	mbination dru	g and combinat	tion index (CI	value).	
sample	mutation	mutations	CI < 1 s	ynergy; = 1 ad	ditive, >1 antago	onsitic effect		
			Cytar- abine	Nelarabine	Gemcitabine	HDAC6 inhibitor (ACY1215)	Vincristine	Dexamethasone

#### 2.3.2. Clinical studies

The clinical study, CB103-C-101 (NCT03422679) was a first-in-human (FIH) trial, open-label phase I/IIA study designed to evaluate safety, tolerability, pharmacokinetics (PK), pharmacodynamics (PD), and preliminary efficacy of CB-103 administered orally in adult patients with either locally advanced or metastatic solid tumours or haematological malignancies characterised by pathogenic activations of the NOTCH signalling pathway.

In cohorts 1-8, CB-103 was given at increasing doses up to 500 mg (free base) once daily (QD). The dose of 500mg QD, given orally, was declared as provisional recommended phase 2 dose (RP2D). Starting with dose group 9, CB-103 was given twice daily (BID). In cohorts 9-12, increasing doses from 250 to 500 mg BID were explored. From dose group 10, an intermittent dosing schedule was introduced whereby CB-103 was administered twice daily on 5 days on treatment followed by two days off treatment break.

The dose of 2x 500mg in an intermittent schedule (five days on treatment, two days off) was declared a safe dose by the Cohort Review Committee (CRC). An MTD was not reached in the study. The 2x 500mg dose in an intermittent schedule (5 days on treatment, 2 days off) was declared as RP2D based on the saturation in exposure observed at this dose level and the high levels of NOTCH target gene downregulation, which would not biologically support further escalating the dose, as well as the signs of clinical efficacy observed. FDA suggests that for  $\geq$  12-year-old adolescent patients no weight-related clinically relevant effect on drug pharmacokinetics or safety are expected,  $\geq$  12-year-old adolescent patients enrolled in this trial may receive the same fixed daily dose as administered in adults (Clinical Growth Charts web page under National Center for Health Statistics at the Centers for Disease Control and Prevention website (https://www.cdc.gov/growthcharts/clinical\_charts.htm).

Overall safety data (N=79) indicates that CB-103 is well tolerated with 61% of all reported adverse events (AEs) being mild (Grade 1) or 27% moderate (Grade 2) in severity, and 11% Grade  $\geq$ 3. Cumulatively, a total of 699 treatment emergent AEs has occurred in 76 patients since study initiation, of which 285 AEs (41%) in 60 patients were considered related to the study drug.

Most of treatment-related AEs resolved without requiring medications or discontinuation of CB-103 dosing, and without sequelae. Overall, there have been no sign of cardiotoxicity and no QTc prolongation reported. The most common study drug-related AEs ( $\geq$ 10%) were

Page | 6 04/25/2024

nausea (21.5%), dyschromatopsia (19.0%), anaemia (16.5%), blurred vision (15.2%), dyspepsia (12.7%), diarrhoea (12.7%), fatigue (11.4%), and vomiting (11.4%).

Three SAEs were considered related to study drug (two drug-induced liver injury in two patients with progressive liver metastasis and Stevens-Johnson syndrome was diagnosed in a patient after she took amoxicillin/clavulanic acid). There were two DLTs. One patient in cohort 8 (500mg) experienced one dose limiting toxicity (DLT). This was an elevation of the gamma-glutamyl transferase (GGT), grade 3, that was asymptomatic and deemed not clinically significant by the investigator. One patient in cohort 11 (400mg BID) experienced visual impairment that led to treatment interruption which counts as DLT. After the patient switched to a once daily schedule, he continued treatment. No deaths due to drug-related AEs have been reported.

Individual patients have been treated with CB-103 under compassionate use in combination with other drugs (anticancer drugs and drugs for the prevention of GVHD). The combination treatment did not alter the safety profile of CB-103 and did not increase or worsen toxicities associated with the combination drugs. There were further signs of efficacy, particularly two patients with r/r T-ALL that achieved complete response.

In addition to demonstrating a favorable safety profile of CB-103, pharmacodynamic data have shown strong target engagement, down-regulation of key target genes as well as long-term stable disease in patients with Notch-pathway activation in Adenoid Cystic Carcinoma (ACC) [10]. Taking together the fact that Notch activation is an important driver of multi-drug resistance [10], the confirmed effect on the target, and exceptional safety profile in cancer patients, CB-103 is an ideal drug to be used in combination with standard of care therapies to tackle multi-drug resistant cancer.

# 2.4. Mitochondrial cell death pathway

The apoptotic blocking provided by BCL-2 expression has been shown to have a central role in survival of leukemic cells [11]. The mitochondrial cell death pathway is initiated by proapoptotic BH3-only effector proteins, which activate the cell death proteins including BAX and BAK [12]. The survival of cells depends on antiapoptotic family proteins (BCL- 2, BCL-X, and MCL1) that bind and sequester BH3-only effector protein, which in turn blocks activation of the cell death pathway.

Using BH3 profiling, a mitochondrial assay that classifies blocks in the intrinsic apoptotic pathway, Moore et al. [13] provided evidence that cells in the ALL samples exhibit dependence on BCL-2 by demonstrating inhibition of BCL-2 and killing of leukemic cells using a proapoptotic pharmacologic inhibitor of Bcl-2/Bcl-xL, ABT-737.

# 2.5. Venetoclax (ABT-199)

Venetoclax (ABT-199) is a novel, orally bioavailable small-molecule inhibitor of B-cell lymphoma 2 (BCL2), a key regulator of the intrinsic apoptotic pathway. Venetoclax has shown promising effects in hematologic malignancies including chronic lymphocytic leukemia (CLL) and acute myeloid leukemia (AML) [14, 15, 16]. Recent preclinical studies have suggested that inhibition of BCL-2 may be a novel therapeutic strategy for patients with T-ALL [17].

Two clinical trials will study the efficacy of venetoclax in monotherapy in RR ALL. A phase I study is recruiting pediatric patients and young adults with RR ALL to address the safety and pharmacokinetics of venetoclax monotherapy (NCT03236857). Another phase 1 study with dose escalation is underway and recruiting participants and will analyze the safety and pharmacokinetics of venetoclax, navitoclax, and chemotherapy in recurrent ALL (NCT03181126).

Page | 7 04/25/2024

[figure not shown]

#### 3. STUDY POPULATION

#### 3.1. Inclusion Criteria:

**3.1.1.** Adolescent (12 to 18 years) and adult (19 to 60 years) patients who have relapsed or refractory T-cell lymphoblastic leukemia (T-ALL) or T-Cell lymphoblastic lymphoma (T-LBL) according to 2017 WHO classification [29] and NCCN v1 2021 [30]:

Patients must have  $\geq 5\%$  blasts in the bone marrow as assessed by morphology on standard bone marrow biopsy and aspirate or less than 5% blasts in the bone marrow in presence of extramedullary relapse, excluding isolated central nervous system (CNS) relapse. However, if an adequate bone marrow sample cannot be obtained, patients may be enrolled if there is unequivocal evidence of leukemia with  $\geq 5\%$  blasts in the peripheral blood.

- **3.1.2.** Patients are eligible independently of Notch pathway activation in the leukemic blasts: however, a fresh marrow/blood sample must be obtained before starting the study treatment to classify the patients as being either Notch positive or negative.
- **3.1.3.** Leukemic blasts must express of at least 2 of the following immune phenotyping: CD1a, CD2, CD3, CD4, CD5, CD7, CD8, CD34, TCR $\alpha$ B, TCR $\gamma$ S, cyCD3
- **3.1.4.** Patients have adequate performance status (ECOG ≤2) for patients ≥16 years old, Lansky score >50 for patients <16 years old.
- **3.1.5.** Patients must be 12 to 60 years of age inclusive when signing the informed consent. For patients < 18 years of age, parent or legally authorized representative (LAR) should be willing and able to give informed consent. Non-English speaking patients are eligible for whom consent process will follow institutional guidelines.
- **3.1.6.** Patients with CNS disease are eligible.
- **3.1.7.** Patients must have adequate organ function and laboratory results (obtained within 14 days of enrollment):
  - **3.1.7.1.** Direct bilirubin  $\leq 2$  x upper limit of normal (ULN).
  - **3.1.7.2.** Serum creatinine  $\leq$  1.5 x ULN; or if serum creatinine > 1.5 x ULN, then serum creatinine clearance (CrCl)  $\geq$  50 mL/min (estimated by Cockcroft-Gault formula).
  - **3.1.7.3.** Alanine aminotransferase (ALT) and/or aspartate aminotransferase (AST)  $\leq$ 3 x ULN;  $\leq$ 5 x ULN in case of suspected leukemic liver involvement

Page | 9 04/25/2024

- **3.1.8.** Females of childbearing potential must have a negative serum or urine beta-human chorionic gonadotropin ( $\beta$ -HCG) pregnancy test result within 14 days prior to the first dose of study drugs and must agree to use one of the following effective contraception methods during the study and for 30 days following the last dose of study drug. Effective methods of birth control include:
  - **3.1.8.1.** Birth control pills, skin patches, shots, subdermal implants
  - 3.1.8.2. Intrauterine devices (IUDs)
  - **3.1.8.3.** Condom or occlusive cap (diaphragm or cervical/vault caps) used with Spermicide
  - **3.1.8.4.** Abstinence
- **3.1.9.** Males agree to inform study doctor right away if their partner becomes pregnant or suspects pregnancy. While in this study and for 30 days after the last treatment the patient agrees not to donate sperm for the purposes of reproduction. He agrees to use a condom while in this study and for 30 days after the last treatment.

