For any significant abnormalities seen at the eye examination, all assessed parameters and findings should be documented in the respective eCRF pages and source documents.

- **8.5. Pregnancy tests and assessment of fertility**: Only female patients of childbearing potential must undergo serum and urine pregnancy tests
- **8.6. Disease assessment**: Disease assessment by bone marrow samples (aspirate and/or biopsy), cytogenetics and flow cytometry is done at baseline screening and at completion of each treatment cycle. A bone marrow biopsy and/or aspirate will be obtained to assess bone marrow cellularity and to determine the percentage of leukemic blasts, including assessment of minimal residual disease (MRD) to confirm remission status.

At the baseline assessment, bone marrow biopsy and/or aspirate is within 3 weeks and no less than 1 day before the first drug dose. Then on each cycle, patients are assessed for disease response by bone marrow biopsy and/or aspirate on day 28. If the blasts in bone marrow are <5% but marrow is hypocellular (cellularity  $\leq$ 15%) on day 28 ( $\pm$ 3 days), then a repeat bone marrow biopsy and/or aspirate is obtained 1 week later to assess response; if residual leukemia is present, repeated bone marrow biopsy and/or aspirate will be obtained as medically indicated.

Only for patients with extramedullary disease or as clinically indicated a PET-CT will be performed at baseline and if positive, also at end of the induction and of the reinduction cycles, and thereafter as clinically indicated. A time window of  $\pm$  3 days is allowed for the tumor assessments. A wider time window is allowed only at baseline; however, assessments should be performed as close as possible to the 1st drug administration and if feasible, not later than 3 weeks prior to the 1st drug administration

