#### 9. RESPONSE DEFINITIONS

Because morphologic examination of the bone marrow during periods of hematopoietic recovery after intensive chemotherapy may be unreliable, a response will be based on blast percentage by flow cytometry. Flow cytometric assessment of response (MRD) should be performed at MDACC. Blast percentages determined by morphology can be used in cases where the sample submitted for flow cytometry evaluation is limited or hemodiluted. Patients will be considered evaluable for response if they have been administered greater than 50% of the dose of CB-103. Patients will be evaluable for safety if they have been administered 1 dose of CB-103.

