#### 9.1.2. Response Criteria T-ALL:

- **9.1.2.1. CR** (Complete Remission): Absolute neutrophil count >  $1.0 \times 10^9$ /L, platelets >  $100 \times 10^9$ /L, red cell transfusion independence, and bone marrow with < 5% blasts. No evidence of extramedullary disease.
- **9.1.2.2. CRi** (CR with incomplete blood count recovery): Bone marrow with < 5% blasts, with peripheral neutrophils of  $\le 1.0 \times 10^9$ /L or platelets  $\le 100 \times 10^9$ /L.
- **9.1.2.3. PR** (Partial Remission): All of the hematologic values for a CR but with a decrease of at least 50% in the percentage of blasts to 5% to 25% in the bone marrow aspirate. No evidence of extramedullary disease.
- **9.1.2.4.** Relapse: Subsequent appearance, after achievement of CR, of  $\geq$  5% blasts in the bone marrow with confirmation by flow cytometry or the development of extramedullary disease after achievement of CR.

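### Marrow entry is judged by morphology but response by flow cytometry, so a patient already below 5% by flow at baseline can count as CR/CRi unchanged

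*Combined protocol and SAP*

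**What the plan says.** **Entry (3.1.1).** The main route is at least 5% "blasts in the bone marrow as assessed by morphology on standard bone marrow biopsy and aspirate". Two other routes exist: "less than 5% blasts in the bone marrow in presence of extramedullary relapse" (isolated CNS relapse excluded), and peripheral blood, where "if an adequate bone marrow sample cannot be obtained, patients may be enrolled if there is unequivocal evidence of leukemia" with at least 5% blasts in the blood.

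**Response method (Section 9).** "a response will be based on blast percentage by flow cytometry". The fallback is limited: "Blast percentages determined by morphology can be used in cases where the sample submitted for flow cytometry evaluation is limited or hemodiluted".

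**Response criteria (9.1.2).**
- CR needs under 5% marrow blasts, neutrophil and platelet recovery, red cell transfusion independence and no extramedullary disease.
- CRi needs under 5% marrow blasts with low neutrophils or low platelets.
- Only PR refers to change: "with a decrease of at least 50% in the percentage of blasts to 5% to 25% in the bone marrow aspirate".

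**Baseline data (8.6).** Bone marrow sampling with "cytogenetics and flow cytometry is done at baseline screening and at completion of each treatment cycle". Flow is thus available before the first dose.

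**Evaluability (Section 9).** "Patients will be considered evaluable for response if they have been administered greater than 50% of the dose of CB-103". No baseline blast condition is attached.

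**The concern.** One 5% line decides who has marrow disease at entry and who has cleared it at response, but it is read by two methods. Nothing in the documents uses the screening flow result for eligibility, for evaluability or as the reference for response.

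Take a patient with 8% blasts by morphology and 3% by flow at screening. The patient is eligible. If flow still reads 3% after the second cycle, the CR/CRi marrow criterion is met although nothing has moved. With low neutrophils or platelets, that is a CRi. CR is harder, because it also needs the counts, transfusion independence and absence of extramedullary disease.

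On the marrow route the error runs mainly upward. Entry selects patients who are high by morphology, so the disagreements that can enter are those low by flow. The reverse kind, below 5% by morphology and at or above 5% by flow, does not qualify through the marrow blast count.

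ORR is the primary efficacy endpoint, and Section 12 needs only 6 responses in 30. One or two such patients can affect the conclusion.

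**Working it through.** **Inputs from Section 12.** Looks at 10, 20 and 30 patients; λ = 0.57, α = 0.86; prior Dir(0.05, 0.1, 0.15, 0.7), which gives Beta(0.15, 0.85) for efficacy and Beta(0.20, 0.80) for toxicity. The null is p_eff 0.15, p_tox 0.20, p_efftox 0.05. The alternative is p_eff 0.30, p_tox 0.10, p_efftox 0.05.

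**Input not in the documents.** The share f of enrolled patients who are at or above 5% by morphology but below 5% by flow at baseline. Assumed range: 0 to 3 in 30.

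**Step 1: reproduce the boundaries.** Stop for futility if Pr(p_eff > 0.15 | data) < 0.57(n/30)^0.86. Stop for toxicity if Pr(p_tox ≤ 0.20 | data) < 0.57(n/30)^(0.86/3).

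| n | Efficacy cutoff | Last stopping count (posterior) | Toxicity cutoff | First stopping count (posterior) |
|---|---|---|---|---|
| 10 | 0.222 | 0 (0.014) | 0.416 | 3 (0.272) |
| 20 | 0.402 | 2 (0.206) | 0.508 | 5 (0.331) |
| 30 | 0.570 | 5 (0.555) | 0.570 | 6 (0.536) |

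These match Table 18.

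**Step 2: reproduce the operating characteristics.** An exact multinomial calculation over the three looks gives a type I error of 8.17%, against 8.34% in Table 19. The simulation standard error with 10000 runs is √(0.0834 × 0.9166 / 10000) = 0.28 points. Exact power is 78.46%, against 77.76%. All ten acceptance rates in Table 19 reproduce within 1 point, so the design arithmetic is sound.

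**Step 3: add discordant patients.** If every discordant patient is counted as CR/CRi and the rest respond at 15%, the apparent ORR is q = f + (1 − f) × 0.15. For f = 1/30, q = 0.0333 + 0.9667 × 0.15 = 0.178. The four cell probabilities are 0.05, q − 0.05, p_tox − 0.05 and 1 − q − p_tox + 0.05, with p_efftox held at 0.05. The same boundaries apply. Here f is a probability per patient, so k in 30 is an expected number.

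| Discordant, k in 30 | Apparent ORR | Acceptable, p_tox 0.20 | Acceptable, p_tox 0.10 |
|---|---|---|---|
| 0 | 0.150 | 8.2% | 21.0% |
| 1 | 0.178 | 14.2% | 34.6% |
| 2 | 0.207 | 20.4% | 48.4% |
| 3 | 0.235 | 25.9% | 60.6% |

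**Step 4: fewer conversions.** If half of the discordant patients are counted as responders and the other half are not, q = 0.5f + (1 − f) × 0.15, which is 0.162, 0.173 and 0.185 for 1, 2 and 3 in 30. At p_tox 0.20 the probabilities are then 10.6%, 13.1% and 15.7%.

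**The case against.** The strongest reply is that the problem may be rare. Entry also requires relapsed or refractory disease and at least two listed immunophenotypic markers (3.1.3). With listed exceptions, it bars chemotherapy within 2 weeks (3.2.13). These conditions narrow the chance that a recovering marrow is taken for relapse. A discordant patient must also stay below 5% by flow through two cycles of relapsed disease and receive more than half of the CB-103 dose. All of this limits the size of the effect. None of it sets a flow threshold at entry, so the gap in the rule remains. MRD is reported separately and the go/no-go criteria are non-binding, so residual disease in a CR would be visible, but the ORR would still count the patient.

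Four stronger readings are tempting and are not supported.

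- *The protocol admits that the methods disagree at entry.* Section 9 doubts morphology during recovery after intensive chemotherapy, as its reason for using flow at response. It says nothing about relapse marrow at screening. The remark on hemodilution is a safeguard against one cause of a falsely low flow value.
- *PR has the same defect.* The natural reading of Section 9 with 8.6 is a decrease from flow to flow. A comparison of morphology with flow is possible only because the text is silent. A patient still at 3% by flow cannot be a PR, which needs 5% to 25%.
- *The false-positive rate rises from 27% to 70%.* The efficacy boundaries alone give 0.267, 0.420, 0.572 and 0.705 for 0 to 3 in 30. Acceptance also needs the toxicity boundary, so these are not the trial's error rates.
- *Such patients should simply be non-responders in the primary analysis.* That would fail an eligible patient whose marrow truly clears. If 3 in 30 are affected and the others respond at 30%, the ORR is 0.9 × 0.30 = 0.27, and power at p_tox 0.10 falls from 78.5% to 71.9%.

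**Conclusion.** The concern holds for CR and CRi. As written, the plan allows a patient who qualified by morphology and was already below 5% by flow to enter the primary ORR as a responder without change. That follows from the text and needs no assumption.

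The size does rest on assumptions: the discordance rate, conversion of every discordant patient to CR/CRi, a true rate of 15% in the others, and p_efftox fixed at 0.05. Under them, one such patient in 30 raises the false-acceptance rate at the design null from 8.2% to 14.2%, and three raise it to 25.9%. A reader might infer that the trial's type I error is 25.9%. The documents do not support that, because they give no discordance rate, and with half conversion the figure is 15.7%. The sample-size calculation itself is correct; the fault lies in the endpoint definition. It should be corrected before response is adjudicated.

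**What to change.** Add to Section 9:

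1. Each patient's marrow response is judged by the same method at baseline and follow-up, using the baseline flow result already collected under 8.6. The PR decrease is flow to flow, or morphology to morphology where morphology is the fallback.
2. For a patient already below 5% by flow at baseline, an unchanged flow reading below 5% does not count as CR or CRi. Marrow response is read by morphology, the method that qualified the patient. A sensitivity analysis reports ORR with these patients counted as non-responders.
3. For patients enrolled on peripheral blood blasts without an adequate marrow sample, state that the same-method rule cannot be applied, and include them in the sensitivity analysis.

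The cost is a few sentences and one CRF field for the baseline flow percentage. No new test is needed. The reported ORR may be slightly lower. If discordance proves rare, the recorded baseline values will let the sponsor show that the ORR is unaffected.
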